We will provide 3 months of additional free clinic visits following the end of this project. At the conclusion of the 3 week study, a non-study clinician in our research clinic will be given the data on the subject's response to L-DOPA. This clinician will discuss with each subject on a case-by-case basis the risks and benefits of continuing L-DOPA treatment as well as other treatment options if warranted. Those who have benefited from the treatment and have not had significant side effects may elect to continue receiving LDOPA after receiving an explanation of the potential risks of chronic administration. If they do not want to continue L-DOPA, it will be discontinued after a 3 day step-down withdrawal of the drug. Transferring after-study care to a non-study clinician protects against the development of bias in the study clinicians and offers optimal clinical care to the subjects at the study conclusion.

Clinical Treatment Alternatives

Clinical treatment alternatives

The alternative to participating in this study is to seek treatment outside the research project. Patients who would rather receive treatment elsewhere will be given referrals to appropriate and affordable care.

Risks/Discomforts/Inconveniences

Risks that could be encountered during the study period

1. Interview, emergencies, and possible suicidal ideation. Subjects may experience discomfort during the clinical interview and evaluations when discussing symptoms and current life events. The study coordinators are experienced and skilled in interviewing depressed subjects. Half-way through the initial assessment, the coordinator will ask the subject if they would like to take a break, and this will be provided if desired. A study clinician will be available during all aspects of the assessment if there are any questions or problems. In addition, should the subject express suicidal ideation at any time during the interview, the

study clinician will be contacted immediately to assess the subject and to determine the appropriate course of action. Options for addressing suicidal ideation will include contacting the individual's mental health caregiver, referring for urgent (same day) evaluation and treatment in an outpatient clinic, or emergency room evaluation and hospitalization. Similar practices will be used for other emergencies, including but not limited to psychosis, homicidal or violent thoughts, or an acute change in a subject's physical status.

2. L-DOPA Side Effects: Side effects will be assessed at each planned visit and if needed through additional or unscheduled contacts. We will attempt to minimize side effects by slow dosage titration and allowance for dose reduction if needed. We will withdraw subjects from the study if they cannot tolerate the lowest dose of carbidopa/levodopa (L-DOPA) 37.5mg/150mg daily.

L-DOPA is a well-tolerated medication at the doses we will be using in this study. Older (i.e., 1960s-70s era) case studies report administering L-DOPA doses of 400-1200mg and in some cases much higher to depressed, non-PD patients over subacute time periods (4-12 weeks). Variable clinical results were observed, but few side effects were reported and no dyskinesias. More recently, a double-blind study (conducted by Co-Investigator [name] and colleagues) of a single dose of L-DOPA 200mg vs. placebo investigated the role of dopamine in the impaired interval timing abilities observed in older adults. Thirty two healthy aged participants aged 71.2 ± 7.6 years were trained to produce two target time intervals (6 and 17 seconds in duration) in separate blocks corresponding to drug/placebo administration. Of the 16 elderly subjects who took 200mg L-DOPA, no severe side effects were noted, and no individuals discontinued participation in the study. Forty-four percent reported mild nausea at some point during the experiment, which was the only side effect noted. There are sporadic other reports in the literature examining the effects of single-dose 200mg L-DOPA on cognitive outcomes in healthy controls (e.g., Rihet et al, Psychopharmacology 2002; Hasbroucq et al, Psychopharmacology 2003), but no other recent (i.e., post 2000) studies have been performed of subacute L-DOPA dosing in healthy controls.

There are many studies of chronic L-DOPA administration for the treatment of PD, since this drug has been used since the 1960s. Perhaps the most relevant recent study was a clinical trial published in the New England Journal of Medicine in 2004 (72). In this study 361 patients with PD were randomized to receive 150mg, 300mg, or 600mg L-DOPA for 40 weeks. In the 150mg and 300mg L-DOPA treatment groups, which are similar to the 100mg and 300mg treatment groups being used in the R61 Phase of this study, the only side effects observed that were different from placebo were headache and nausea. No dyskinesias or other neuropsychiatric effects were observed that were greater than the placebo group, and this study lasted 40 weeks as opposed to 3 weeks in the R61 Phase of this study. Despite these reassuring data, and recognizing that we include a different patient population, we will carefully assess subjects with new complaints to determine if they may be related to study drug and if there is a need for closer monitoring or change in study drug dosing.

- a. L-DOPA common side effects: In patients taking L-DOPA for the management of bradykinesia and freezing associated with PD, the most common side effects are dyskinesias (i.e., choreiform, dystonic, and other involuntary movements) and nausea.
- b. Other L-DOPA side effects: blood pressure changes, orthostasis, anorexia, dyspepsia, constipation, psychotic episodes (e.g., delusions, hallucinations), vivid dreams, and nightmares.

- c. Discontinuation Syndrome: A neuroleptic malignant-like syndrome (fever, akinetic crisis, rigidity, autonomic disturbances) has been reported following withdrawal of levodopa in patients with PD.
- 3. PET imaging—Radiation Exposure: The dose of radiation will be submitted for approval to the Columbia University Medical Center Joint Radiation Safety Committee (JRSC). All scans will be done in the presence of medical supervision and trained nursing staff in an institution specifically designed to support imaging studies. In the event of serious medical complications, the PET scan facilities have immediate access to, or consultation with, specialized medical units at the Columbia University Medical Center (CUMC). Preparation of radiopharmaceuticals and performance of PET scans will be by radiochemists, physicians, and technologists of the Department of Radiology, Columbia University Medical Center. These professionals are qualified by training and experience in the safe use and handling of radiopharmaceuticals. Subjects will be asked about their previous radiation exposure and those who have had research exposure within the past year will be excluded if their cumulative annual exposure (including the present study) exceeds FDA limits. The study doctor will be informed regarding subjects' previous radiation exposure.

Dose estimates indicate that the maximum, permissible single study dosage of [11C]-raclopride in human subjects, to remain below the CFR 361.1 dose limits for research subjects, is 42.8 mCi (i.e., calculation based upon gallbladder as the critical organ; 5 rads per single study limit and 0.117 rads per mCi to the gallbladder). Thus, a dose of max 14 mCi per injection, and the dose associated with participation to this study (2 injections: 28 mCi) will be within this limit. Subjects will be instructed not to participate in any other research studies that include radiation exposure during the year starting on the day of the first study. Subjects exposed to radiation in the work place are excluded, as well as subjects exposed to nuclear medicine procedures during the previous year, including research protocols.

- 4. PET imaging—The dose of raclopride used in this study is negligible (equal or below 6.94 µg per administration) and is expected to induce less than 5% occupancy of D2 receptors. [11C]raclopride is a radiotracer that has been extensively used to measure striatal D2 receptors both in the US and in Europe. Side effects have never been reported at the tracer doses used in PET studies. In addition, unlabeled raclopride has been tested at pharmacological doses in humans, as a potential antipsychotic drug. Its safety and tolerability have been well characterized (Farde et al., 1989; Farde et al., 1988; Cookson et al., 1989; The British Isles Raclopride Study Group, 1992) Therefore, we do not anticipate any pharmacological effects from the radiotracer used in the proposed studies. As with any drug, the possibility of idiosyncratic reaction exists and is mentioned in the consent forms. A physician is present at each experiment.
- 5. Magnetic Resonance Imaging: Although this procedure is generally low-risk, there are particular concerns. Individuals will be screened for the presence of implanted metal (including but not limited to medical devices, shrapnel, tattoos or permanent makeup). Those who screen positive will be excluded from the study. Claustrophobia is also an issue for many potential subjects. During the MRI, subjects will have voice contact with a radiology technician, and they may request the scan be stopped at any time.
- 6. Incidental Findings: Magnetic Resonance Imaging: Another risk is the occurrence of incidental findings on MRI. All scans are reviewed at time of acquisition and concerning findings are discussed with an attending neuroradiologist. Should any concerning findings be seen, the site PI will convey these findings to

the subject along with recommendations for further evaluation, and facilitate referrals for such evaluation and treatment.

- 7. Breach of confidentiality: There is the potential risk of breach of confidentiality of clinical, genetic, and laboratory information. [name] has extensive experience as a clinical investigator in dealing with sensitive information and assuring that data is adequately protected. Safeguards to protect confidentiality include locked records and firewalls around password-protected electronic data, and all study data being coded, with the key linking the code with a subject's identity being kept in a separate, locked file.
- 8. a. Risks of placing an intra-venous catheter. Drawing blood from and inserting an intravenous line (IV) into an arm vein are safe and standard medical procedures. Sometimes a bruise will occur at the puncture site and rarely a blood clot or infection will occur in the vein. Certain individuals may feel light-headed during venipuncture. The volume of blood collected during this study, include screening laboratories, will be approximately 2-3 tablespoons. These are not expected to have any serious negative effects on the study participants. b. Risks of blood draw: In the obtaining a 20 cc blood sample, patients can experience side effects that include pain, fainting, bruising, light-headedness, and, on rare occasions, infection. The staff will take every precaution to avoid these difficulties. The staff members are all certified at the hospital to be drawing blood from patients, and are instructed to keep the comfort and welfare of our patients as their primary priority.
- 9. Gait speed assessment: During the gait speed assessment, patients may feel unsteady and as such their risk of falls may increase. To mitigate these risks, patients are accompanied by research coordinators and/or doctors during each of the performance-based assessments. Coordinators walk slightly behind and alongside the patients during the gait assessment, providing support for the patients should they become unsteady during the procedure.

Describe procedures for minimizing risks

- 1. The study coordinators are experienced and skilled in interviewing subjects with a variety of mental health issues. Half-way through the initial assessment, the coordinator will ask the subject if they would like to take a break, and this will be provided if desired. A study clinician will be available during all aspects of the assessment if there are any questions or problems. In addition, should the subject express suicidal ideation at any time during the interview, the study clinician will be contacted immediately to assess the subject and to determine the appropriate course of action. Options for addressing suicidal ideation will include contacting the individual's mental health caregiver, referring for urgent (same day) evaluation and treatment in an outpatient clinic, or emergency room evaluation and hospitalization. Similar practices will be used for other emergencies, including but not limited to psychosis, homicidal or violent thoughts, or an acute change in a subject's physical status.
- 2. Side effects will be assessed at each planned visit and if needed through additional or unscheduled contacts. We will attempt to minimize side effects by slow dosage titration and allowance for dose reduction if needed. We will withdraw subjects from the study if they cannot tolerate the lowest dose of carbidopa/levodopa (L-DOPA) 37.5mg/150mg daily.

- 3. The dose of radiation will be submitted for approval to the JRSC. All scans will be done in the presence of medical supervision and trained nursing staff in an imaging center specifically designed to support imaging studies. In the event of serious medical complications, the PET scan facilities have immediate access to a consultation with specialized medical units at New York Presbyterian Hospital. Preparation of radiopharmaceuticals and performance of PET scans will be by radiochemists, physicians, and technologists of the Department of Radiology at Columbia. These professionals are qualified by training and experience in the safe use and handling of radiopharmaceuticals. Subjects will be asked about their previous radiation exposure and those who have had research exposure within the past year will be excluded if their cumulative annual exposure (including the present study) exceeds FDA limits. The information on the previous radiation exposure of study subjects will be notified to the study doctor.
- 4. In terms of raclopride pharmacologic effects, we do not anticipate any pharmacological effects from the radiotracer used in the proposed studies. As with any drug, the possibility of idiosyncratic reaction exists and is mentioned in the consent forms. A physician is present at each experiment.
- 5. To minimize MRI risks, each subject will fill out the MRI Safety Questionnaire before the study. Only subjects who fulfill the criteria by this questionnaire will be eligible for the study. In addition, subjects will remove all metal (watch, hair pins, jewelry) before entering the MRI room. If the subject has any metallic prostheses/implants they will be excluded from the study. If a subject becomes anxious during the scan they can request that the MRI scan be stopped.
- 6. [name] has extensive experience as a clinical investigator in dealing with sensitive information and assuring that data is adequately protected. Safeguards to protect confidentiality include locked records and firewalls around password-protected electronic data, and all study data being coded, with the key linking the code with a subject's identity being kept in a separate, locked file.
- 7. Risks of bruising, clotting, and infection during IV placement and blood draw will be minimized by having venipuncture performed by trained and experienced personnel under sterile conditions. To avoid injury due to fainting, the antecubital vein catheter will be inserted when the subjects are recumbent.
- 8. The staff will take every precaution to avoid difficulties with gait speed assessments. Patients are accompanied by research coordinators and/or doctors during the test of gait speed. Coordinators walk slightly behind and alongside the patients during the gait assessment, providing support for the patients should they become unsteady during the procedure.

Methods to Protect Confidentiality

Describe methods to protect confidentiality

All records of the participating subjects will be kept in a locked room with access provided only to staff members. Patients' names will be linked with code numbers in a password protected file to which only the research assistant has access. Only these code numbers will appear on all pill bottles and paper measures collected during study. All data collected will be kept confidential and used for professional purposes only.

Publications using these data will be done in a manner that protects the subjects' anonymity. All electronically stored data will be accessible by password known only to the principal investigator and research assistants for the study.

Data shared with the National Institute of Mental Health Data Archive (NDA) will maintain patient confidentiality by ensuring exclusion of all 18 identifiers (outlined by HIPAA) prior to data sharing.

Will the study be conducted under a certificate of confidentiality? No

Direct Benefits to Subjects

Direct Benefits to Subjects

There is no direct benefit to subjects. If L-DOPA treatment is effective in ameliorating slowing, subjects may experience improved quality of life and decreased of falls and other sequelae of slowing.

Compensation and/or Reimbursement

Will compensation or reimbursement for expenses be offered to subjects?

Yes

Please describe and indicate total amount and schedule of payment(s).

Include justification for compensation amounts and indicate if there are bonus payments.

Subjects will receive reasonable reimbursement for transportation related costs associated with study involvement as long as they provide receipts.

Subjects will receive \$25 for each weekly study visit (Week 0, Week 1, Week 2, and Week 3) attended. This money will be paid by cash at the conclusion of each of these visits for a total of \$100 if all study visits are attended.

Subjects will receive \$50 for each MRI scan (\$100 total for the MRI) and \$150 for completing each PET scan (\$300 total for PET). Of note, subjects will be compensated for scheduled scans if they are brought to the MRI or PET suites and the scans are not completed that day due to chemistry failure or other similar issues.

Thus, subjects undergoing neuroimaging may earn \$400 in this study, which will be a lump sum payment mailed in the form of a check at the conclusion of the study, plus an additional \$100 cash (\$25 cash at the end of each weekly visit) if all weekly study visits are also completed. If a subject does not complete the study, payment is pro-rated to portions completed. Subjects are advised to allow 1-3 weeks for receipt of payment for neuroimaging.

References

References

- 1. NIH Consensus Conference. Diagnosis and treatment of depression in late life. JAMA 1992; 268:1018–1024.
- 2. Rothschild AJ. The diagnosis and treatment of late-life depression. J Clin Psychiatry 1996; 57:5–11.

Descriptive statistics are expressed as means and standard deviations or percentages. Chi-square analyses and independent samples t-tests were used to analyze dose dependent increases in processing and gait speed. Also the changes in Hamilton Rating Scale for Depression.

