Individuals with Late Life Depression (LLD) often have cognitive problems, particularly problems with memory, attention, and problem solving, all of which contribute to antidepressant non-response. Our group and others have shown that decreased thinking speed is the central cause of functional problems in patients with LLD. Similarly, decreased walking speed is associated with depression and carries additional risk for falls, hospitalization, and death. Available evidence suggests that declining functionality in the brain's dopamine system contributes to age-related cognitive and motor slowing. The central hypothesis of this R61/R33 Phased Innovation Award is that by enhancing dopamine functioning in the brain and improving cognitive and motor slowing, administration of carbidopa/levodopa (L-DOPA) will improve depressive symptoms in older adults.

This IRB protocol pertains to the R61 Phase of this grant proposal, and a separate IRB will be submitted subsequently for the R33 Phase. In the R61 Phase 60 adults aged > 60 years with (1) a DSM 5 depressive disorder, (2) significant depressive symptoms, (3) decreased thinking speed, and (4) decreased walking speed will receive 3 weeks of treatment with L-DOPA up to 450mg. We will test whether L-DOPA increases brain dopamine release using neuroimaging and whether it speeds up thinking and walking speed. If L-DOPA treatment achieves these goals, we will proceed to compare the best-tolerated dose of L-DOPA to placebo in the R33 Phase.

Data collected in the proposed studies may help identify a new treatment for LLD, which could have large public health ramifications given the prevalence, frequent treatment resistance, and chronicity characteristic of LLD. This project also will elucidate the neurobiology of slowing at molecular, structural, and functional levels of analysis, increasing our understanding of the interplay between these aging-associated processes and the pathophysiologic changes underlying late life neuropsychiatric disorders. Exploring patient characteristics that predict response to L-DOPA may provide useful information to guide differential therapeutics and develop personalized medicine for LLD.

Background, Significance and Rationale

Background, Significance and Rationale LLD affects 3% of community-dwelling adults over 60 years old (1), and 15% of older adults have

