Hypothesis 2: 150mg, 300mg, and 450mg L-DOPA will increase processing and gait speed, with greatest improvement occurring at the 450mg dosage level.

Exploratory aims: To obtain information on the dosing and tolerability of L-DOPA in our patient population as well as identify PET and MRI biomarkers associated with slowing.

Description of Subject Population

Sample #1

Specify subject population

adults aged >59 years with a depressive disorder, decreased processing speed, and decreased gait speed Number of completers required to accomplish study aims

48

Projected number of subjects who will be enrolled to obtain required number of completers

Age range of subject population 60 years or older

Gender, Racial and Ethnic Breakdown

On the basis of previous depression studies conducted in the Adult and Late Life Depression Research Clinic, it is anticipated that the sample will be composed of 60% women and 40% men as well as approximately 75% Caucasian, 15% African American, and 10% Hispanic subjects.

On the basis of previous depression studies conducted in the Adult and Late Life Depression Research Clinic, it is anticipated that the sample will be composed of 60% women and 40% men. Description of subject population

This phase will enroll 60 outpatients who (1) are aged \geq 60 years, (2) diagnosed with Diagnostic and Statistical Manual (DSM) 5 (107) MDD, Dysthymia, or Depression Not Otherwise Specified (NOS), (3) have Center for Epidemiologic Studies-Depression Rating scale (CES-D) (108) score \geq 10, (4) have decreased gait speed (defined as average walking speed over 15' course \leq 1m/s), and (5) are willing to and capable of providing informed consent and complying with study procedures.

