- 16. Drs. [name] and [name] continue to be Co-Investigators responsible for neuroimaging as part of a subcontract executed between RFMH and SUNY-Stony Brook. They will lead analyses of neuroimaging data. In terms of on-site execution of PET and MRI scans, these are supervised by the study PI ([name]) and/or [name], who works with the Aging Program as a study clinician and has a research background in PET neuroimaging.

Clinical treatment

- 16. An effort will be made for all subjects to be titrated up to 450mg L-DOPA over a 3 week-duration study. We chose 450mg as the target dose because it is higher than doses known to affect cognition (i.e., 150-300mg) but lower than levels used for PD (i.e., 600-1200mg) that may have greater side effects. Each subject will start taking 37.5mg carbidopa/150 mg levodopa (1.5 25/100 sinemet tablets) once daily for one week, then increase to 75mg carbidopa/300mg levodopa (1.5 25/100 sinemet tablets twice daily) for one week, and finally increase to 112.5mg carbidopa/450mg levodopa (1.5 25/100 sinemet tablets three times daily) for one week. Each subject will be titrated to 450mg L-DOPA unless they cannot tolerate higher doses, in which case subjects will have their dosage reduced to the maximum tolerable dose.
- 17. Although each subject is titrated up to 450mg L-DOPA if it is tolerated, the study design allows us to assess the effects and tolerability of three different L-DOPA doses (150mg, 300mg, and 450mg). Based on published work using L-DOPA for PD, we expect effects on cognition and gait to be apparent at each dosing level approximately 5 days after dosage increases. By performing assessments weekly, we will thus obtain measures of L-DOPA's effect on processing and gait speed at each dosing level. We carefully reviewed the literature and consulted our Co-Investigator [name] (neurologist and PD expert) for evidence of carry-over effects of L-DOPA dosing (such that prior experience with 150mg and 300mg may influence a subject's experience of receiving 450mg). We found little evidence to suggest there are significant carry-over effects from previous L-DOPA doses, so each dose will be able to be assessed on its own merits. Similarly, we do not anticipate that the repeated assessments of processing and gait speeds will bias the study results.

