- 18. In selecting L-DOPA doses, we balanced appropriate safety concerns regarding the use of this medication in a novel patient population with the goal of causing a measurable effect. L-DOPA is an extremely well tolerated medication at doses < 600mg, which is substantially less than the doses often reached in the treatment of Parkinson's disease (900-1200mg). L-DOPA has been administered to healthy subjects in single dose studies and found to be well-tolerated. In Parkinson's disease, a recent clinical trial published in the New England Journal of Medicine randomized patients to receive 150mg, 300mg, or 600mg L-DOPA for 40 weeks. In the 150mg and 300mg L-DOPA treatment groups, the only side effects

observed that were different from placebo were headache and nausea. No dyskinesias or other neuropsychiatric effects were observed that were greater than the placebo group. In terms of effects, single-dose studies have reported significant effects on cognition and neural activation with L-DOPA doses as low as 100mg. Thus, we believe the 150-450mg dose range to be used in this study will be both safe and likely to produce an observable effect.

Assessments

- 19. Subjects are expected to have a screening/evaluation visit, PET/MRI scanning day (for those receiving imaging), and weekly visits from Week 0-3.
- 20. At baseline, we will record each subject's chief complaint, referral source, age of onset of mood and/or cognitive decline, number prior depressive episodes, age, sex, marital status, race and ethnicity, years of education, employment status and income, years of education, family history. We also will document medical history, physical exam, urine drug screen, CBC, chemistries and electrolytes, thyroid profile, vitamin B12 and folate levels, urine analysis, and ECG. Vital signs will be measured at baseline and monitored weekly throughout the study. The Cumulative Illness Rating Scale-Geriatric (CIRS-G) (112) will be filled out at baseline to measure chronic medical illness burden. Subjects' current physical pain will be assessed weekly using a 100mm Pain Visual Analog Scale (VAS) and used as a covariate in analyses of gait speed (113).

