- 21. The following measures will be collected weekly throughout the study: 24-item HRSD, CGI Severity and Improvement, Structured Pill Count Interview, Unified Parkinson's Disease Rating Scale (UPDRS) (questions 32 and 33 will be used in this study to assess the duration and disability of dyskinesias caused by L-DOPA), Treatment Emergent Side Effect Scale, and Inventory of Depressive Symptoms—Self Report (IDS-SR).
- 22. In addition, processing and gait speed assessments will be performed weekly at 1pm to control for time of day effects and the duration since the last morning L-DOPA dose (anticipated to be 4 hours). Processing speed will be assessed using the Digit Symbol test from the Wechsler Adult Intelligence Scale-III (WAIS-III) (119) and the Pattern and Letter Comparison tests (120). These tests are all reliable and valid, with moderate to high loadings on the latent speed factor. A latent factor (and subsequent factor score) will be extracted from the 3-test battery pre- and post-treatment and used as the main outcome in the R61. By extracting a latent factor and factor loadings we will utilize a more pure measure of processing speed than if we used the raw scores from an individual test or a sum total score from the three raw scores combined (121-124).
- 23. Gait will be assessed as both a single and dual task (ST, DT) on a 15' walking course in the LLDC. For the ST, patients are instructed to walk at their usual or normal speed over the 15' walking course. For the DT, patients are instructed to walk at their usual pace while simultaneously verbally listing as many animals as possible (fluency DT). In addition, a counting DT will be used in which patients are instructed to walk at their usual pace while simultaneously performing serial subtractions by threes starting at 100 (125). Patients will start and end at a point 2 meters from beginning of the 15' course to eliminate acceleration and deceleration effects. Each ST and DT will be assessed two times with the average used in the analyses. The ST assessment of walking speed in m/s will be used as the primary outcome measure for this study.

End of study procedures

24. Following the 3 week duration treatment study, endpoint assessments will be made. Patients will enter 3 month open treatment period provided free of charge as described below.

You can upload charts or diagrams if any

Criteria for Early Discontinuation

Criteria for Early Discontinuation

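### The tests named for processing and gait speed (chi-square, independent-samples t) do not fit a one-group, within-subject dose titration

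*Combined protocol and SAP*

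**What the plan says.** The Statistical Analysis plan section is three sentences long. The first covers descriptive statistics. The second is the only place in the documents that names a test for the speed outcomes: "Chi-square analyses and independent samples t-tests were used to analyze dose dependent increases in processing and gait speed". The third is a fragment that appears to extend the second to the HRSD.

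The protocol describes the design those tests are applied to:

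- **One group, all doses in sequence.** Clinical treatment, item 16: "Each subject will be titrated to 450mg L-DOPA unless they cannot tolerate higher doses". Item 17 says the weekly visits are meant to give L-DOPA's "effect on processing and gait speed at each dosing level".
- **Repeated continuous outcomes.** Assessments, item 22: "processing and gait speed assessments will be performed weekly at 1pm". The same item makes a processing speed factor score the main outcome. Item 23 says of single-task gait: "The ST assessment of walking speed in m/s will be used as the primary outcome measure for this study".
- **No comparator in this phase.** The Lay Summary defers it, on condition that the goals are met: "we will proceed to compare the best-tolerated dose of L-DOPA to placebo in the R33 Phase".
- **A covariate for gait.** Assessments, item 20, has pain measured weekly on a "100mm Pain Visual Analog Scale (VAS) and used as a covariate in analyses of gait speed".
- **The hypothesis under test.** Specific Aims, Hypothesis 2: "150mg, 300mg, and 450mg L-DOPA will increase processing and gait speed, with greatest improvement occurring at the 450mg dosage level".

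The Summary of Experiences to Date reports, at 450 mg, ES 0.41 with p = 0.001 for processing speed and ES 0.43 with p = 0.003 for dual-task gait, from 36 participants with 8.3% drop-out. It does not define ES or give the n behind either test.

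**The concern.** Hypothesis 2 compares each dose with the same person's own baseline. An independent-samples t-test needs two sets of different people, and this phase has one set seen four times (Weeks 0 to 3). Chi-square needs categories, and both outcomes are continuous. Neither test can adjust for pain, so the commitment in item 20 cannot be met by the stated method.

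The stake is traceability. The processing speed factor score and single-task gait are the outcomes the protocol ranks highest, and the one sentence on how they were tested cannot be right for this design. A reader cannot tell which analysis produced the reported p-values, or whether pain was in the gait analysis.

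**Working it through.** **Step 1. Design against method (no assumption needed).**

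| Feature of the design | Unpaired t-test | Chi-square |
|---|---|---|
| Same people at each visit | Treats them as different people | Not designed for this |
| Continuous score or m/s | Suitable type | Not applicable |
| Pain covariate for gait | Cannot include it | Cannot include it |
| No second group | Needs two independent groups | Nothing to cross-classify |

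**Step 2. Direction of the error if the unpaired test was really used.** With common SD s and within-person correlation r, the variance of a mean change is 2s²(1 − r)/n. The unpaired test uses 2s²/n. For r > 0 this is too large, so the test is conservative and inefficient. It does not create false positives.

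**Step 3. Do the reported p-values follow from the stated test?** Inputs from the Summary of Experiences: ES 0.41 and 0.43; n = 36; drop-out 8.3%, which equals 3/36 and would leave 33. Assumptions: ES is a mean difference divided by the between-person SD, n is 33 to 36 at each visit, and the test is two-sided.

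Unpaired: t = ES × √(n/2), df = 2n − 2.

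| Outcome | n per visit | t | df | p | Reported p |
|---|---|---|---|---|---|
| Processing speed | 36 | 0.41 × √18 = 1.739 | 70 | 0.086 | 0.001 |
| Processing speed | 33 | 0.41 × √16.5 = 1.665 | 64 | 0.101 | 0.001 |
| Dual-task gait | 36 | 0.43 × √18 = 1.824 | 70 | 0.072 | 0.003 |
| Dual-task gait | 33 | 0.43 × √16.5 = 1.747 | 64 | 0.086 | 0.003 |

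One-sided testing gives 0.043-0.050 and 0.036-0.043. At 36 per visit the unpaired test would need ES of about 0.81 and 0.725 to reach the reported p-values. At the reported ES it would need about 132 and 98 people per visit. Under these assumptions the reported values do not reproduce.

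**Step 4. Would a paired test give them?** Paired, with ES on the between-person SD: t = ES × √(n / (2(1 − r))), df = n − 1. Setting t to the critical value c for the reported p gives r = 1 − n × ES² / (2c²).

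- Processing speed, n = 36: c = 3.591, r = 1 − 36 × 0.1681 / (2 × 12.90) = 0.77. With n = 33: r = 0.79.
- Dual-task gait, n = 36: c = 3.190, r = 1 − 36 × 0.1849 / (2 × 10.18) = 0.67. With n = 33: r = 0.70.
- If fewer people were measured at 450 mg, r must be higher. At n = 28, an illustrative value, it is 0.83 and 0.76.

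These correlations are plausible for repeated performance tests, but they are solved from the p-values. They show that a paired reading is possible; they do not confirm it.

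**Step 5. Other meanings of ES.**

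- ES on the SD of the change, paired: t = ES × √n, giving p = 0.019-0.025 and 0.014-0.019. Neither matches.
- ES as Cohen's f, unpaired: t = 2 × ES × √(n/2), giving 0.0009-0.0014 for processing speed, which rounds to 0.001. Gait gives 0.0005-0.0009, which does not match 0.003.

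**Step 6. A check on the reporting.** The PET results in the same summary do reproduce as tests of change against zero on 24 df: t = −4.85, −2.52 and 0.265 give p = 0.00006, 0.019 and 0.793. So a within-subject test that the SAP does not mention appears to have been used for PET. This says nothing direct about the speed outcomes.

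**The case against.** The strongest reply is that the SAP sentence is a loose summary of a completed analysis, the analysts probably did something sensible, and the p-value argument proves little. Much of this stands. ES is undefined, n per test is not given, and dose reduction was allowed, so fewer than 33 people may have been at 450 mg. A Cohen's f reading recovers the processing speed p-value under the unpaired test, and the paired match needs a chosen denominator and a fitted r. The SAP is also not the only text bearing on these analyses, since the protocol describes the latent factor, the averaging of two gait trials and the pain covariate. It is, however, the only text that names a test.

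None of this rescues the sentence. The mismatch in Step 1 holds whatever ES means and whatever n was.

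Two stronger readings are tempting. A reader might infer that the reported significance is spurious. The documents do not support that: a plausible paired analysis gives the reported values, and an unpaired one would err towards missing an effect. A reader might also infer that the decision to proceed to the R33 phase is unsound. The Specific Aims refer to thresholds for that decision but the documents do not state them, so no effect on it can be shown.

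**Conclusion.** The concern holds as a mismatch between the stated tests and the design, and that part rests on no assumption. The gap in p-values (0.086-0.101 against 0.001; 0.072-0.086 against 0.003) is supporting evidence only. It depends on ES being a standardised mean difference on the between-person SD, and on 33 to 36 people per visit. The likeliest reading is that the SAP misdescribes what was done. Correction and disclosure are required because the sentence is the only stated method for the main outcomes. The case for correction does not rest on any demonstrated error in the results.

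**What to change.** 1. Correct the SAP sentence to state the analysis actually run for processing speed, each gait measure and the HRSD: test, sidedness, n per visit, the SD used as the ES denominator, and whether pain VAS was in the gait analysis. Complete the HRSD fragment. Keep chi-square for categorical variables only.
2. If the analysis was unpaired, or left out pain for gait, re-run it on the existing data with a within-subject method. One suitable choice is a linear mixed or other repeated-measures model on Weeks 0 to 3, with dose-minus-Week-0 contrasts and 95% confidence intervals, and pain VAS included for gait. A paired test is also acceptable for processing speed. Label the re-run as specified after results were known, and report which results change.
3. Report single-task gait, the stated primary measure, beside the dual-task result.

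The cost is a wording change and disclosure, plus a re-analysis only under item 2. The Status section says only data analysis is still under way, so the correction can still be made. No participants or procedures are affected.
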